Self-Monitoring (SM) Assessments: Throughout the study, participants will complete assessments via the conversational interface of the mobile app. At the beginning of the intervention (T0), participants will complete a baseline assessment focused on their current engagement in- and perception of-healthy behaviors (eating habits and physical activity level). This assessment will be adapted from the Patient Health Engagement (PHE) Scale⁴⁸. The same questions regarding patient engagement will also be asked at each assessment time point (T1 – T3). The DWN will prompt the participants daily to use the SM feature of the mobile app to complete an assessment that will determine their daily implementation of the physical activity tasks and cognitive behavioral skills learned. For example, participants will be asked to complete a food log that documents the amounts of fruits and vegetables, junk food, water, protein, and whole grains consumed each day. These food types and their suggested quantities are detailed in the nutrition education learning modules. The DWN will also conduct weekly assessments, initially only asking participants to weigh themselves and record their body fat. As the intervention progresses, in collaboration with the CHW they will also be asked to set their weekly treatment goals and reflect on their goals from the past week (barriers that prevent them from reaching their goals and if they need to modify their goals). As a part of SM component, the caregiver and CHW are notified when the AAAO submits or misses submitting an assessment. Once an assessment is submitted, the caregiver reviews the adolescent's progress. If the AAAO does not submit the required assessment or if the caregiver does not review one, the CHW is alerted, and they have the option to reach out directly to the participants through the messaging feature.

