Physical Activity (PA): In W1, participants begin wearing the Fitbit wearable provided and set their step count goals during the weekly assessment. In addition, four CBST video categories will demonstrate the independent PA workouts the participants will perform weekly: 1) Warm-up (5 minutes); 2) High intensity interval training for cardiovascular fitness (20 minutes); 3) Resistance band and body weight resistance training (20 min); and 4) Cool down with yoga stretches (5 minutes). Participants will perform these PA workouts while wearing their Fitbit. The number of client workouts during the week depends on their PA goals set during the weekly assessment. The DWN provides textual and visual feedback on the client's step count and workout sessions. As a part of the PA component of the intervention, the caregiver and CHW are notified when the AAAO receives this feedback, at which time the former reviews the adolescent's progress. If the AAAO does not meet their PA goals or if the caregiver does not review the feedback, the CHW is alerted, and they have the option to reach out directly to the participants through the messaging feature. The AAAO and caregiver will receive Fitbit Inspire 3s, resistance bands, a yoga mat, and a Body Composition Scale as a part of the study. The equipment will be returned to the investigator at the end of the intervention phase.

Contingency Management (CM): The CM feature provides financial incentives to attend sessions and to encourage families to meet the following weekly goals (\$10 per goal): step count, nutrition SM, CBST education, and PA participation. Caregivers have the opportunity to receive bonus incentives (\$50 for completion over three consecutive weeks, maximum 3 bonuses over study duration) for reviewing the AAAO's PA participation and nutrition SM entries. AAAOs may also receive bonus incentives using the same pay structure (\$50) for every four consecutive weeks of at least a one-pound weight reduction. Session attendance (telehealth visit with CHW) is also incentivized at \$50 per session for the AAAO and caregiver, individually. CM

goals will be released along with the accompanying CBST material so that families have adequate knowledge to apply the prescribed strategies. Successful attendance and completion of all goals (including bonuses) over the 12-week period results in a total value of \$1230. Incentives will be disbursed as reloadable debit cards (ClinCard).

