Adverse and Serious Adverse Events. Any adverse events (AEs) or serious adverse events (SAEs) that are observed and/or reported will be immediately reported to PI [name]. An adverse event is any reaction, side effect or untoward event that occurs during the course of the study. Adverse events are categorized as serious (see below) or non-serious, as related or not related to the study intervention, and as expected or unexpected. For the purpose of the present trial, clinically insignificant events will be excluded from any type of AE documentation. These include colds, flu, cuts, scrapes, coughs, headaches, stomach complaints, general fatigue and mild symptoms. Behavioral AEs that will be tracked in this trial include injury due to physical activity or increases in adolescent behavior problems or family conflict. Serious adverse events (SAEs) are defined as deaths, life-threatening events, permanently or substantially disabling events, congenital anomalies, events

requiring an initial hospitalization or prolonging a current hospitalization, or events that require intervention to prevent permanent impairment or damage. Participants will be screened for AEs and SAEs at each study data collection visit except baseline. AEs and SAEs will be formally elicited at each scheduled data collection point, using an AE Worksheet that will include the expected AEs discussed above and general probes for other physical or behavioral difficulties since the last study contact. AEs that are reported to research staff at times other than those detailed above (e.g. during a phone call to schedule data collection, while working with the computer) will also be recorded and reported as described below. All clinically significant AEs will be categorized as an SAE or non-SAE, as expected or unexpected, and as likely or unlikely to be related to the study treatment by the Co-I or his designate. The Co-I will review all AE reports for concurrence regarding relatedness to the intervention, seriousness, and appropriate resolution. The Co-I or his designate will track all SAEs until resolution has been achieved. All SAEs and AEs will be entered into the study database so that they may be reported to the data and safety monitor. If an SAE is determined to be related to the intervention, then it will be reported to the Data and Safety Monitoring Officer in real time (within 48 hours of occurrence or identification by study personnel).

DSMP Administration

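### Adolescents are paid for weight loss, but excessive weight loss and disordered eating are not named on the AE Worksheet and are elicited only through general probes

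*Protocol*

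**What the plan says.** **The payment.** Under Contingency Management (section 3.0), adolescents can earn a $50 bonus "for every four consecutive weeks of at least a one-pound weight reduction". Full attendance and completion, bonuses included, is stated to be worth $1230 over 12 weeks.

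**The weight data.** Section 3.0 (Self-Monitoring) has participants weigh themselves in a weekly app assessment. Section 9.0 (Aim 1, Methods) collects BMI and percent overweight weekly from a supplied digital scale.

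**The adverse events.** Section 11.0 states: "Behavioral AEs that will be tracked in this trial include injury due to physical activity or increases in adolescent behavior problems or family conflict". The form to be used is described as an "AE Worksheet that will include the expected AEs discussed above and general probes for other physical or behavioral difficulties". On timing, the same section says that "AEs and SAEs will be formally elicited at each scheduled data collection point".

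**The alerts and notices.** In section 3.0, "the caregiver and CHW are notified when the AAAO submits or misses submitting an assessment". Further, "If the AAAO does not submit the required assessment or if the caregiver does not review one, the CHW is alerted". For exercise, "If the AAAO does not meet their PA goals or if the caregiver does not review the feedback, the CHW is alerted". Section 2.0 adds a notice to the CHW when a family is not adhering.

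**The concern.** The trial pays 12-to-17-year-olds for losing weight and follows their weight every week. Losing too much or too fast, and restricting food to do it, are foreseeable harms of that payment. The protocol fixes what the AE Worksheet asks about, and neither harm is on the named list. The risk section (12.0) mentions only embarrassment and release of personal information, so it does not fill the gap.

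At stake is whether staff put a direct question to the adolescent and caregiver. A general probe depends on the family seeing the behavior as a difficulty and volunteering it. An adolescent who is restricting food may not do so, and a family pleased with the weight loss may not see a problem.

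**Working it through.** **1. Size of the payment (inputs from section 3.0).**
- Weekly goals: 4 goals x $10 x 12 weeks = $480
- Session attendance: $50 x 12 = $600
- Adolescent weight bonus: 12 / 4 = 3 periods, 3 x $50 = $150
- Total: $480 + $600 + $150 = $1230, which matches the stated figure
- Share tied to weight loss: 150 / 1230 = 12.2%

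The caregiver's three review bonuses also come to $150, so the caregiver's total is $1230 as well. The match is consistent with three weight bonuses per adolescent.

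**2. What earns the bonus.** The wording can mean one pound in each of four weeks or one pound over the four weeks. Collecting all three bonuses then needs at least 3 x 4 x 1 = 12 lb, or 3 x 1 = 3 lb. Both are minimums. No maximum is stated.

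**3. What is asked.** Section 11.0 names three kinds of event. None concerns weight or eating. Both harms therefore fall to the general probes.

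**4. How often it is asked.** The protocol does not define a scheduled data collection point. Two readings are possible:
- T1 to T3: 16 adolescents x 3 = 48 screens, 12 / 3 = 4 weeks apart
- Weekly: 16 x 12 = 192 screens, 1 week apart

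On either reading, no screen carries a named question on weight loss or eating.

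**5. What the other safeguards respond to.**

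| Safeguard | Section | Responds to |
|---|---|---|
| Non-adherence notice | 2.0 | too little adherence |
| Self-monitoring alert | 3.0 | missed or unreviewed assessment |
| Exercise alert | 3.0 | unmet goal or unreviewed feedback |
| Submission notice, caregiver review | 3.0 | the fact of submission; review has no stated criterion |
| Weekly CHW session | 3.0, 9.0 | goals, steps, calories, modules; weight is not a listed item |
| CHW note of % body fat | 9.0, schedule of measures | recorded weekly, no action level |
| Data inspection | 11.0 | random each week, thorough each quarter |
| Entry exclusion where weight loss is contraindicated | 4.0 | status at entry |

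An adolescent who over-restricts, logs every day and meets every goal sets off none of the described alerts. A person may still notice through the contact and review rows.

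**The case against.** The strongest reply is that nothing is closed off. Section 11.0 defines an AE broadly enough to cover both harms, its list of tracked events is introduced as inclusive, and the general probes cover physical and behavioral difficulties. With 16 adolescents and 2 CHWs (about 8 each), someone is in contact with each family every week, is notified of each submission and can see the dashboard. That stands, and it limits the point to how directly the question is asked.

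Four stronger readings are tempting, and the documents do not support them:

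- **Such events would go unreported.** They are reportable under the general definition, and anything observed or reported goes to the PI at once.
- **Nobody would see a rapid fall.** Submission notices, caregiver review, weekly sessions and the body-fat note all give someone the chance. What is missing is a rule tied to the weight value.
- **The scheme rewards fast loss.** The bonus is flat, so losing more than the minimum earns nothing extra. The absence of an upper limit is still true.
- **Leaving the harms unnamed would upset their classification.** The protocol says "All clinically significant AEs will be categorized as an SAE or non-SAE, as expected or unexpected", and a case off the list could be classed as unexpected. No described reporting step depends on that class: 48-hour reporting turns on seriousness and relatedness.

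It can also be said that disordered eating belongs under behavior problems. It may, but the text does not say so.

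**Conclusion.** The point holds in a narrow form. The protocol pays adolescents up to $150 (12.2% of the maximum) for weight loss with no ceiling, and the AE Worksheet as described has no named item on excessive weight loss or disordered eating. Both are elicited only through general probes. Other safeguards could catch a case, but none is aimed at one.

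This is a cheap, optional improvement to participant safety. It affects no estimate, test or sample size. The number of cases at stake cannot be estimated, because the documents give no event rate and no level of loss that counts as excessive.

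Two assumptions matter. The worksheet is not shown, so the point rests on the protocol's description of it. A separate safety monitoring document or the worksheet may already name these items, in which case only the protocol text needs aligning.

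**What to change.** **Main change.** In section 11.0, add *excessive or rapid weight loss* and *disordered eating* to the events named for tracking, so that both appear on the AE Worksheet and are asked about at every AE elicitation.

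**Secondary change.** At each weekly session, have the CHW look at the adolescent's weight change since the previous week and refer to the PI any fall faster than a rate the investigators set before enrollment. The weights are already collected. This means at most 16 x 12 = 192 looks over the trial, or 16 x 11 = 176 if no starting weight precedes week 1. If AE screens are held only at T1 to T3, it shortens the gap between checks from about 4 weeks to 1. If they are weekly, it only makes the check specific. This step is secondary because the documents offer no basis for the rate.

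**Cost.** One edited sentence, two more worksheet questions, one line in the session routine, and an occasional false referral from home-scale error. The number of false referrals cannot be estimated, since neither the rate nor the scale's error is given. Bonuses, design and analysis stay as they are.

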12.0 Risks to Subjects

Risks of participation in the proposed study are considered to be minimal. Two potential risks have been identified as possible outcomes for participants. These risks pertain to (1) embarrassment regarding participation in the study, or (2) distress if personal information obtained during the assessment were released to outside parties. All information obtained from participants will be confidentially maintained, with only legal obligations to report instances of child abuse and neglect, threat of harm to self or others, as explained in the informed consent, leading to release of participant information to the appropriate authorities.

13.0 Potential Benefits to Subjects or Others

We believe the benefits of our proposed study outweigh the minimal risks associated with participation. This work aims to increase access, adherence and engagement in healthy behaviors for obese African American adolescents. All participants (CHWs, caregivers) will be informed that their data will be used to inform the scientific understanding of within-session therapy processes to improve healthcare outcomes. It is possible that CHWs and caregivers in the proposed study will benefit from providing questionnaire and physiological data, if such activities provide opportunities to reflect upon their treatment experience. Furthermore, this research, if successful, could provide effective, low-cost, automatic, provider fidelity assessment and feedback systems that could be used to transport any evidence-based treatment to real-world underserved racial/ethnic minorities living in under-resourced communities, who seldom receive evidence-based treatments that they so desperately they need.

References

1. Davis, K. K. *et al.* Racial differences in weight loss among adults in a behavioral weight loss intervention: Role of diet and physical activity. *J Phys Act Health* **12**, 1558–1566 (2015).
2. *From Crisis to Opportunity Reforming Our Nation's Policies to Help All Children Grow Up Healthy*. 2. <https://media.stateofobesity.org/wp-content/uploads/2021/10/12132618/State-of-Childhood-Obesity-10-13-21-Final-WEB.pdf> (2021).
3. Williams, W. M., Yore, M. M. & Whitt-Glover, M. C. Estimating physical activity trends among blacks in the United States through examination of four national surveys. *AIMS Public Health* **5**, 144 (2018).

4. Overweight and physical activity among children a portrait of states and the nation 2005. (U.S. Department of Health and Human Services, Health Resources and Services Administration, 2005).
5. Skinner, A. C., Perrin, E. M., Moss, L. A. & Skelton, J. A. Cardiometabolic Risks and Severity of Obesity in Children and Young Adults. *New England Journal of Medicine* **373**, 1307–1317 (2015).
6. Daniels, S. R. The consequences of childhood overweight and obesity. *Future Child* **16**, 47–67 (2006).
7. Must, A. & Strauss, R. S. Risks and consequences of childhood and adolescent obesity. *Int J Obes* **23**, S2–S11 (1999).
8. Reilly, J. J. Descriptive epidemiology and health consequences of childhood obesity. *Best Pract Res Clin Endocrinol Metab* **19**, 327–341 (2005).
